Before administration of propofol, remifentanil infusion at a rate of 0.05 µg/kg/min was started. Five minutes after start of remifentanil infusion, an attending anesthesiologist administered propofol (1 mg/kg) mixed with lidocaine (1 mg/kg) over 1 minute followed by continuous infusion of propofol on the basis of clinical signs of arousability, movement, blood pressure, heart rate and respiratory rate in a spontaneous breathing child. Two independent investigators assessed the level of sedation using the clinical sedation scale such as UMSS and the modified Observer's Assessment of Alertness/Sedation (MOAAS) every minute during induction and maintenance of sedation (Table 1). MOAAS includes only the responsiveness component of the original OAA/S (5). These two observers performing the clinical sedation score assessments were blinded to the BIS monitor throughout study period. Another third investigator recorded the BIS and EMG values, oxygen saturation, respiratory rate, blood pressure and heart rate immediately before each assessment of clinical sedation score. The BIS and EMG values with a signal quality index (SQI) ≥ 50 were accepted for analysis. Deep sedation was defined based on clinical sedation scale categories: a UMSS score of 3-4 or a MOAAS score of 0-1.

Statistical analysis plan

Document Date: April 30, 2017

Uploaded: June 10, 2018

The sample size was calculated with α error of 0.05 and a power of 80% to determine the validity of BIS values to detect deep sedation in children with cerebral palsy. A minimum 19 participants was required to detect a correlation coefficient of 0.6 for repeated measures. We enrolled 22 patients, taking into consideration of 15% drop-out rate.

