Statistical analysis was performed with SPSS version 22.0 (SPSS Inc, Chicago, IL, USA) for Windows. Continuous variables were presented as mean \pm standard deviation for normal distributed data or the median and interquartile range for non-normal distributed data after the Kolmogorov-Smirnov test with Lilliefors correction. Categorical variables were presented as number of patients (%). The BIS values at each UMSS and MOAAS score were compared using one-way ANOVA followed multiple pairwise comparisons with Bonferroni correction. BIS values were categorized into ranges of <50, 50-59, 60-69, 70-79, 80-89 and 90 or higher. The Kappa was calculated to determine the agreement between the BIS value categories and clinical sedation score between 2 independent observers. A kappa ≥ 0.7 was considered good agreement. The correlation between the paired BIS value categories and clinical sedation scores was determined by Spearman rank correlation test. Receiver operating characteristic (ROC) curve analysis was performed to determine the sensitivity and specificity of BIS for predicting deep sedation based on clinical sedation scores. A cut-off BIS value for detecting deep sedation in children with CP was also calculated. A p value of 0.05 was considered to be statistically significant.

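### The ANOVA comparison of BIS between sedation levels makes no provision for unequal spread, so its pairwise error rates are unprotected, in a direction the documents cannot settle

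*Combined protocol and SAP*

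**What the plan says.** The combined document's statistical analysis plan (unnumbered) sets the comparison out in one sentence: "The BIS values at each UMSS and MOAAS score were compared using one-way ANOVA followed multiple pairwise comparisons with Bonferroni correction". The significance rule is "A p value of 0.05 was considered to be statistically significant".

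The same section foresees non-normal data. Its response is limited to presentation: continuous variables are shown as mean and SD, "or the median and interquartile range for non-normal distributed data after the Kolmogorov-Smirnov test with Lilliefors correction". Nothing links the result of that check to the choice of test. The section has no check of equal variances, no unequal-variance version of the ANOVA or of the pairs, and no robust standard errors.

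The study protocol has both scales scored every minute through induction and maintenance, with BIS recorded just before each score. It defines deep sedation as UMSS 3-4 or MOAAS 0-1. Neither part states how many readings are expected at each level, or the SD of BIS at any level. Pooling of the variance is not stated either; it is the ordinary meaning of one-way ANOVA with Bonferroni pairs.

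**The concern.** A pooled-variance pairwise test gives every pair the same SD, averaged over all levels and weighted by their size. If the two levels in a pair are noisier than that average, the standard error is too small and false positives exceed the nominal rate. If they are quieter, the test is conservative and loses power.

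Unequal spread and unequal level sizes are both plausible here. Sedation starts with a propofol bolus over one minute followed by an infusion, for a procedure done under deep sedation, so intermediate levels may be brief. The top BIS band is 90 or higher, where awake readings might bunch while transitional readings spread. These are inferences, not figures in the plan.

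At stake is the reliability of statements that BIS does or does not differ between adjacent levels, notably UMSS 2 v 3, the step into deep sedation.

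**Working it through.** **The plan's own figures.** The only calculation given is for a correlation: "A minimum 19 participants was required to detect a correlation coefficient of 0.6 for repeated measures". Two-sided Fisher z gives ((1.960 + 0.842)/0.693)² + 3 = 19.3. With the bias term, z = 0.693 + 0.6/36 = 0.710 at n = 19, and power is Φ(0.710 × √16 − 1.960) = Φ(0.88) = 0.81, so 19 reproduces. Also 19 × 1.15 = 21.85, giving 22. Neither figure bears on the ANOVA, for which the plan states no error rate or power.

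**Inputs**
- From the plan: one-way ANOVA, Bonferroni pairs, significance at 0.05.
- Assumed: five UMSS levels (0 to 4), so 10 pairs and a per-pair level of 0.05/10 = 0.005 (two-sided, critical z = 2.807); readings per level 150/30/40/300/100 (620 in all); independent readings; the SD patterns below.

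**Formulas**, for levels i and j with equal true means:
- pooled variance = Σ(n − 1)SD² / (620 − 5)
- SE used = pooled SD × √(1/nᵢ + 1/nⱼ)
- true SE = √(SDᵢ²/nᵢ + SDⱼ²/nⱼ)
- actual error = 2 × [1 − Φ(2.807 × SE used / true SE)]

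**Example, SDs 5/10/12/10/8, UMSS 2 v 3**
- Pooled variance = (149×25 + 29×100 + 39×144 + 299×100 + 99×64)/615 = 48,477/615 = 78.8, so the pooled SD is 8.88.
- SE used = 8.88 × √(1/40 + 1/300) = 1.49.
- True SE = √(144/40 + 100/300) = 1.98.
- The critical value acts as 2.807 × 0.753 = 2.115, so the error is 0.034.

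**Same steps, other SD patterns**

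| SDs at UMSS 0-4 | Pooled SD | SE used, 2 v 3 | True SE, 2 v 3 | Error 2 v 3 | Error 3 v 4 |
|---|---|---|---|---|---|
| all 10 | 10.00 | 1.68 | 1.68 | 0.005 | 0.005 |
| 8/10/11/10/9 | 9.46 | 1.59 | 1.83 | 0.015 | 0.0041 |
| 5/10/12/10/8 | 8.88 | 1.49 | 1.98 | 0.034 | 0.0035 |
| 4/10/14/10/8 | 8.94 | 1.50 | 2.29 | 0.065 | 0.0033 |
| 3/12/16/10/6 | 8.92 | 1.50 | 2.59 | 0.104 | 0.0005 |
| 6/9/9/10/10 | 9.08 | 1.53 | 1.54 | 0.0052 | 0.011 |
| 5/8/9/12/12 | 10.36 | 1.74 | 1.58 | 0.0020 | 0.015 |
| 5/8/8/12/10 | 9.96 | 1.68 | 1.44 | 0.0011 | 0.0080 |

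The last three rows keep a tight awake level, yet 2 v 3 is near nominal or conservative and 3 v 4 is liberal. The direction is set by the SDs.

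**Which ingredient matters.** With 660 assumed readings in levels of 22/33/55/220/330 and equal means, simulation gave:
- Equal SDs: overall F error 0.049. A bounded, skewed but identical distribution at every level: 0.046. Neither the scale limit nor unequal sizes does harm by itself.
- Unequal SDs: F error from 0.016 to 0.356, and familywise error of the pairs from 0.016 to 0.313.
- With equal level sizes (132 each) the overall rates stay at 0.054 to 0.063 for F. A single pair can still be off: with 124 readings per level, the 5/10/12/10/8, 4/10/14/10/8 and 3/12/16/10/6 patterns give 0.018 to 0.028 for 2 v 3.

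**Separate from clustering, and not cured by it.**
- For 22 children with 30 readings each, equal SDs and assumed intraclass correlations of 0.1, 0.3 and 0.5, the planned F has error 0.146, 0.391 and 0.548. Welch gives 0.150, 0.387 and 0.553, so it repairs nothing there.
- For 22 children with 29 readings each and a child-effect SD of 6, removing child effects but keeping one residual variance left the 2 v 3 error at 0.037, 0.066 and 0.102 for the same three patterns. Robust errors gave 0.008 to 0.010. A second check of this kind gave 0.035 to 0.096, and about 0.006 with cluster-robust errors.

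**The case against.** The strongest reply is that the harm is hypothetical. The documents give no level sizes, no SDs and no duration of maintenance, and pooled variance is itself an inference. This stands, and it limits what can be said.

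A reader might infer that the p value for UMSS 2 v 3 is too small and that for UMSS 3 v 4 too conservative. The documents do not support either direction: SDs of 5/8/9/12/12 reverse both. A reader might also infer that a bounded or non-normal BIS scale invalidates the ANOVA. With equal spread it does not.

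A second reply is that the obvious substitutes are imperfect. This also stands. Welch's F was slightly liberal (0.073 to 0.076) on bounded, skewed data with equal spread and unequal sizes. Rank tests are also sensitive to unequal spread: Mann-Whitney with 40 v 300 readings at a nominal 0.005 gave 0.008, 0.014 and 0.019 for SDs of 12, 14 and 16 v 10. Switching to ranks so that the test matches displayed medians would not settle the matter.

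A third reply is that clustering is the larger defect and that no stated decision rule uses these pairs. Both are true. The sample size rests on a correlation, and the validity conclusions rest on Spearman and ROC. But repairing clustering with a single residual variance leaves the present problem in place.

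**Conclusion.** The point holds in conditional form. The plan commits to a comparison that, in its usual reading, assumes one variance across sedation levels, and it provides nothing for the case where that fails. Under the assumed sizes and independent readings, the UMSS 2 v 3 error at a nominal 0.005 ranges from about 0.001 to 0.10, and it is nominal when SDs are equal. Even the mild pattern 8/10/11/10/9 gives about 0.015, three times nominal. All sizes, SDs and intraclass correlations are assumptions. The documents do not show that the error rates are in fact wrong, or in which direction. The consequence is confined to the ANOVA and its pairs; the Spearman and ROC results do not use the pooled variance.

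**What to change.** Replace the one-way ANOVA with a child-level model of BIS on sedation level, fitted for UMSS and MOAAS separately: a mixed model, or GEE with child as the cluster. Use cluster-robust standard errors, preferably with a small-sample correction given only 22 clusters, or fit a separate residual variance for each level. Keep the Bonferroni adjustment of the pairs. Report n and SD of BIS at each level so that a reader can see whether spread differs.

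Do not rely on Welch ANOVA with Games-Howell pairs alone, since it still treats repeated readings from one child as independent, and do not make a rank-based test the remedy.

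This is a free improvement. It needs no more children or readings, only revised wording in the statistical analysis plan and a re-run of one analysis.

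### Holm step-down would be a cheap, low-priority gain over Bonferroni for the pairwise BIS comparisons, but only on p values from a model that accounts for repeated readings per child

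*Combined protocol and SAP*

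**What the plan says.** The statistical analysis plan states: "The BIS values at each UMSS and MOAAS score were compared using one-way ANOVA", followed by "multiple pairwise comparisons with Bonferroni correction". It singles out no pair of levels, so the natural reading is all pairs within each scale. The general threshold is given as: "A p value of 0.05 was considered to be statistically significant".

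The study protocol defines deep sedation as "a UMSS score of 3-4 or a MOAAS score of 0-1". Both scales are scored every minute in each child, and the ANOVA is described without any term for child.

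The sample size rests on a correlation, not on a pairwise difference: "A minimum 19 participants was required to detect a correlation coefficient of 0.6 for repeated measures". The SAP states no power for any pairwise test. Deep sedation itself is addressed by ROC analysis with a BIS cut-off.

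**The concern.** On an ordered sedation scale, most pairs of levels lie far apart and will be rejected almost regardless of the threshold. Single-step Bonferroni still charges every pair the same share of alpha. The pair that straddles the deep-sedation line (the deepest non-deep level against the lightest deep level) bears most directly on the study's aim, yet it gets no more alpha than awake against deepest.

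Holm starts at the Bonferroni threshold and relaxes it each time a hypothesis is rejected. The easy pairs therefore hand their alpha on to the harder ones. What is at stake is an avoidable non-significant result at the boundary, which could be read as BIS failing to separate moderate from deep sedation.

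**Working it through.** **Inputs from the documents.** Two-level definition of deep sedation; readings every minute; alpha 0.05; minimum 19 children, 22 enrolled.

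**Assumed inputs.** The number of levels (the scale table is not in the text available): UMSS 0-4, so 5 levels and 10 pairs; MOAAS 0-5, so 6 levels and 15 pairs. BIS means, SD, readings per level and intraclass correlation (ICC) are also assumed.

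**1. The plan's own figure.** The Fisher z formula for one correlation is n = ((1.960 + 0.842)/atanh 0.6)² + 3. With atanh 0.6 = 0.693, n = 19.34, against 19 stated. For dropout, 19 × 1.15 = 21.85, so 22 as stated (19/0.85 = 22.35 would give 23). Nothing here depends on the pairwise tests.

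**2. Thresholds.** Bonferroni per pair: 0.05/10 = 0.0050 and 0.05/15 = 0.0033. Holm for 10 pairs: 0.0050, 0.0056, 0.0063 and so on to 0.025 and 0.05.

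**3. Power with one mean per child per level.** 20,000 simulated studies, 19 children, independent SD 10, paired t tests. Level means were 95/85/75/(75−g)/(67−g), or 95/88/82/75/(75−g)/(67−g) for six levels, where g is the gap at the boundary.

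| Pairs | Gap g | Bonferroni | Holm | Gain (points) |
|---|---|---|---|---|
| 10 | 5 | 7.8% | 19.6% | 11.8 |
| 10 | 7 | 19.2% | 40.5% | 21.3 |
| 10 | 9 | 37.4% | 64.4% | 27.0 |
| 15 | 9 | 31.0% | 50.9% | 19.9 |

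With all means equal, simulated familywise error is about 4% for both methods. With only the boundary pair truly null, its false rejection is 0.5% with Bonferroni and 1.6% with Holm, both below 5%. A rerun gave the same figures within about one percentage point.

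**4. Power under the ANOVA as written, readings treated as independent.** The standard error of a difference is √(2 × 10²/n). For n = 100 per level it is 1.41, so a 7-point gap is 7/1.41 = 4.95 standard errors, against a Bonferroni critical value of 2.81. Simulated power is 98% against 99.8%. At 50 readings per level it is 75% against 94%. The gain shrinks as information per level grows.

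**5. What clustering does.** Suppose readings cluster by child and level with ICC 0.3. The design effect is 1 + (m − 1) × 0.3, where m is the number of readings per child per level: 2.2 for m = 5 and 3.7 for m = 10. The ANOVA then understates the standard error by √2.2 = 1.48 or √3.7 = 1.92. For a boundary pair with no true difference:

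- Bonferroni: the effective critical value is 2.81/1.48 = 1.89 or 2.81/1.92 = 1.46, giving false rejection of about 6% or 14%.
- Holm, once the other nine pairs are rejected, tests at 0.05: 1.96/1.48 = 1.32 or 1.96/1.92 = 1.02, giving about 19% or 31%.

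Simulation agrees: 5-14% with Bonferroni and 18-32% with Holm. With no differences at any level and ICC 0.1-0.5, familywise error is 12-74% (5 levels) or 12-81% (6 levels), identical for the two methods.

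**The case against.** The strongest case against is that the plan contains no error here. Bonferroni is valid and conservative, no passage names or powers a moderate-against-deep comparison, and the question of detecting deep sedation is answered by the ROC analysis. A non-significant pairwise test would leave the cut-off, sensitivity, specificity, correlation and kappa as they are. All of this stands, and it limits the point to an optional refinement.

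Three stronger readings are tempting, and the documents do not support them.

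- *A reader might infer that Bonferroni is a mistake.* It is not. The only charge is lost power on tests that the plan does intend to run and judge at 0.05.
- *A reader might infer that power at the boundary is 19% as planned and would become 41%.* Those figures belong to an analysis on child-level means with every child reaching every level. The SAP describes an ANOVA of BIS values and gives no SD, gap or readings per level.
- *A reader might infer that changing one word is free.* On the ANOVA as written, the change can raise false rejections at the boundary. Holm also lacks the simple matching simultaneous confidence intervals that Bonferroni has, although the SAP promises none.

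One caution cuts the other way. The inflation in step 5 assumes clustering by child and level. A purely additive child effect, balanced across levels, would make the ANOVA conservative instead.

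**Conclusion.** The point holds as a low-severity, inexpensive improvement. Given valid p values, Holm is never less powerful than Bonferroni and controls the same familywise error. The direction of the gain is certain; its size is not. It is about 20 to 27 percentage points at the boundary with 19 child-level means, SD 10 and a 7 to 9 point gap, and near zero when effective information per level is large. It depends on assumed level counts, means and SD.

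The condition matters as much as the gain. Holm should not be applied to p values from an analysis that ignores repeated readings within a child. In that setting neither method secures 5%, and Holm can add false rejections.

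**What to change.** 1. Replace the one-way ANOVA with an analysis that accounts for repeated readings per child, for example a mixed model with a child-by-level term, or one mean per child per score level.
2. Apply Holm step-down instead of Bonferroni to the resulting pairwise p values, separately within UMSS and within MOAAS, and state that all pairs are tested.
3. Report each estimated difference, the boundary contrast included, with a 95% confidence interval labelled as unadjusted, beside the Holm-adjusted p value.

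**Cost.** Step 2 alone is a change of wording and uses the same p values. Step 1 is a larger change to the SAP and must come first. No new data or larger sample is needed. What is given up is the simple simultaneous intervals that go with Bonferroni. If the data have already been analysed under the stated plan, present the Holm results as a labelled supplementary analysis, so that the method does not look chosen after the fact.

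### The kappa sentence compares BIS ranges with sedation scores, which is not a valid agreement measure; kappa and its 0.7 rule belong to observer-versus-observer agreement, with the weighting stated

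*Combined protocol and SAP*

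**What the plan says.** The Statistical analysis plan section forms six BIS categories: "BIS values were categorized into ranges of <50, 50-59, 60-69, 70-79, 80-89 and 90 or higher". It then states: "The Kappa was calculated to determine the agreement between the BIS value categories and clinical sedation score between 2 independent observers". One decision rule follows: "A kappa ≥ 0.7 was considered good agreement". The next sentence gives the relation between BIS ranges and scores to a different method: "The correlation between the paired BIS value categories and clinical sedation scores was determined by Spearman rank correlation test".

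The Study Protocol section describes who measured what. Two investigators scored UMSS and MOAAS each minute: "These two observers performing the clinical sedation score assessments were blinded to the BIS monitor throughout study period". BIS came from one other person: "Another third investigator recorded the BIS and EMG values". Deep sedation is "a UMSS score of 3-4 or a MOAAS score of 0-1".

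Neither section says which two ratings form the kappa table, whether kappa is computed for each scale, how BIS ranges correspond to score levels, or whether kappa is weighted. Table 1, cited for the scales, is not reproduced in the text available for review.

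**The concern.** A kappa compares two ratings made on the same categories. This sentence names three things (BIS ranges, a clinical score, two observers) and then applies one threshold to the result. A reader of a reported kappa could not tell whether it describes the reliability of the reference standard or the validity of BIS.

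If the sentence is followed as written, the statistic is not a valid agreement measure. If inter-observer agreement was meant, the wording is wrong and the missing weighting can still decide the label. Observer reliability matters because the clinical scores define deep sedation for the ROC analysis.

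**Working it through.** **The plan's own figure.** The plan gives no kappa calculation to reproduce. Its sample size statement is "A minimum 19 participants was required to detect a correlation coefficient of 0.6 for repeated measures". With two-sided alpha 0.05 and 80% power, Fisher's z gives n = ((1.960 + 0.842)/atanh(0.6))² + 3 = (2.802/0.693)² + 3 = 19.34. Simulated power of the t-test for r at n = 19 is 81.3%, so 19 is reproduced. The calculation concerns a correlation, so kappa plays no part in it.

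**Literal reading: BIS ranges versus score.** UMSS 3-4 and MOAAS 0-1 both mean deep sedation, so UMSS rises as BIS falls and MOAAS falls with BIS. Kappa = (p_o − p_e)/(1 − p_e), where p_o is observed and p_e chance agreement. Two six-level examples with equally used BIS ranges show the dependence on coding:
- Perfectly inverse coding: p_o = 0, p_e = 1/6, kappa = (0 − 1/6)/(5/6) = −0.20.
- Perfectly monotone, shifted up one category, with the top two ranges sharing the top level: p_o = 1/6, p_e = (1/6)(4/6 + 2/6) = 1/6, kappa = 0.00, while Spearman is 0.99.

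The simulation assumes MOAAS 0-5, UMSS 0-4, equal level frequencies, mean BIS evenly spaced from 45 to 95, normal error, a cap at 98, and 200,000 pairs per scenario. Codings are aligned with BIS: MOAAS against bins 0-5, and reversed UMSS with one adjacent pair of bins merged.

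| Error SD | Spearman | Unweighted kappa | Quadratic kappa |
|---|---|---|---|
| 20-24 (near design value) | 0.57-0.66 | 0.16-0.24 | at most 0.65 |
| 8-16 | 0.73-0.91 | 0.24-0.54 | 0.71-0.90 |

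Near the planned correlation every version misses 0.7. At stronger correlations the weighting decides the label.

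**Inter-observer reading.** Assume that each observer reads the true level with probability p and otherwise an adjacent level, and that all levels are equally frequent. For UMSS (five levels) at p = 0.80:
- Exact agreement is 0.64 + 2(0.10)² = 0.66 at the three interior levels and 0.64 + 0.20² = 0.68 at the two ends. So p_o = (3 × 0.66 + 2 × 0.68)/5 = 0.668.
- Each observer's marginals are 0.18, 0.22, 0.20, 0.22, 0.18, so p_e = 2(0.18²) + 2(0.22²) + 0.20² = 0.2016.
- Unweighted kappa = (0.668 − 0.2016)/(1 − 0.2016) = 0.58.
- Observers differ by one level with probability 0.320 and by two with 0.012. The mean linear disagreement is (0.320 + 2 × 0.012)/4 = 0.086, against 0.3876 by chance: 1 − 0.086/0.3876 = 0.78.
- The mean quadratic disagreement is (0.320 + 4 × 0.012)/16 = 0.023, against 0.235 by chance: 1 − 0.023/0.235 = 0.90.

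| Scale, level frequencies | p | Exact agreement | Unweighted | Linear | Quadratic |
|---|---|---|---|---|---|
| UMSS, equal | 0.80 | 67% | 0.58 | 0.78 | 0.90 |
| UMSS, equal | 0.85 | 74% | 0.67 | 0.83 | 0.93 |
| MOAAS, equal | 0.80 | 67% | 0.60 | 0.82 | 0.93 |
| MOAAS, equal | 0.85 | 74% | 0.68 | 0.86 | 0.95 |
| UMSS, 2/3/5/70/20% for 0-4 | 0.90 | 82% | 0.65 | 0.73 | 0.84 |
| MOAAS, 30/60/4/2/2/2% for 0-5 | 0.90 | 82% | 0.68 | 0.79 | 0.90 |

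With equal frequencies, 82% agreement passes under every weighting (0.77-0.97). With the assumed deep-weighted frequencies in the last two rows, the unweighted version fails at the same agreement.

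**The case against.** The strongest reply is that the intent is plain. BIS had a single recorder, so the phrase about two observers can apply only to UMSS and MOAAS, and Spearman already covers BIS ranges against scores. On this view there is a drafting slip plus an unstated weighting, and the mapping and scale-direction problems never arise. Most of this stands: inter-observer agreement is the likelier reading. It remains an inference, because the sentence makes BIS categories a term of the agreement, and someone following it would compute an invalid statistic.

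A second reply is that no remedy should prescribe a weighting. This also stands in part. Quadratic weighting is lenient: in the equal-frequency model, 42% exact agreement on UMSS still gives 0.76 quadratic, against 0.27 unweighted. Because the plan is written in the past tense with enrolment complete, choosing the most lenient version now as the only basis for the label would be a post hoc choice.

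A reader might infer that the study's conclusions about BIS rest on a faulty statistic. The documents do not support that: the planned ANOVA, Spearman, ROC and cut-off analyses are specified without kappa.

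**Conclusion.** The point holds as a minor specification error. As written, the sentence applies kappa and the 0.7 rule to categories that are not shared. On the likelier reading it is still wrong to name BIS categories, and the label is not determined until the weighting is stated.

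On the literal reading near the design correlation, unweighted kappa is about 0.16-0.24 and quadratic at most 0.65. Failing 0.7 there would reflect coding and the height of the threshold on a different scale from the planned correlation, so it would say little about whether BIS tracks sedation. On the inter-observer reading, 67-74% exact agreement on UMSS fails unweighted (0.58-0.67) and passes linear (0.78-0.83) or quadratic (0.90-0.93).

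These figures show sensitivity and do not predict trial results. They rest on assumed numbers of levels, level frequencies and error patterns, none of which the visible text gives. It would go too far to infer that good exact agreement, such as 82%, makes the weighting irrelevant; that depends on how often each level is used. Nor can it be said that no mapping exists anywhere, since Table 1 is not shown. The harm is confined to this statistic and its label.

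**What to change.** Reword the kappa sentence so that it, and the 0.7 rule, apply only to observer 1 versus observer 2, separately for UMSS and for MOAAS. Drop the kappa of BIS ranges against scores and rely on the planned Spearman and ROC analyses for BIS.

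Report unweighted and weighted kappa with exact percent agreement, and name the weights. State which version the 0.7 rule judges, and do not let the quadratic version alone carry the label. Give a 95% confidence interval by resampling children, because the minute-by-minute assessments within a child are not independent.

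The cost is a wording change and one statistic re-run on existing data. The downside is that the good-agreement label may become less favourable.

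### The only planned correlation uses six BIS bins instead of the recorded BIS value, so it discards within-bin differences and depends on unexplained cut points

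*Combined protocol and SAP*

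**What the plan says.** The Study Protocol has the BIS number taken down by a dedicated person just before each sedation assessment: "Another third investigator recorded the BIS and EMG values". Readings with a signal quality index of at least 50 go into the analysis.

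The SAP then groups these numbers: "BIS values were categorized into ranges of <50, 50-59, 60-69, 70-79, 80-89 and 90 or higher". No reason is given for these boundaries. The next analysis described is the kappa, which needs categories. After it comes the only correlation in the plan: "The correlation between the paired BIS value categories and clinical sedation scores was determined by Spearman rank correlation test".

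Elsewhere the plan keeps BIS as a number: "The BIS values at each UMSS and MOAAS score were compared using one-way ANOVA". The ROC analysis and its cut-off are also described for BIS, with nothing to suggest bins.

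The sample-size paragraph rests on a correlation: "A minimum 19 participants was required to detect a correlation coefficient of 0.6 for repeated measures". It does not say which coefficient is meant, or whether BIS is recorded or binned.

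**The concern.** Spearman's method replaces each value by its rank, so it already copes with skewed or bounded data such as BIS. Binning first adds nothing and removes information. A reading of 51 and one of 59 become equal, and so do 20 and 49. The open-ended bottom range matters most, because in a study of deep sedation it may hold a large share of the readings.

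Two consequences follow. The coefficient describes a coarser variable than the one in the ANOVA, although a reader may well take it as the association between BIS itself and sedation score. It also changes with where the boundaries are placed, and the plan does not justify them. If the 0.6 used for sizing was meant for recorded BIS, any attenuation from binning also lowers the power of the analysis actually planned.

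**Working it through.** **1. The plan's own figure.** Inputs from the SAP sample-size paragraph: α = 0.05, power 80%, r = 0.6. Sidedness is not stated; two-sided is assumed.

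- Fisher z: n = ((1.960 + 0.842) / atanh 0.6)² + 3 = (2.802 / 0.693)² + 3 = 19.34, rounded up to 20.
- The one-sided version gives 15.87, rounded up to 16, which does not match.
- A simulated two-sided t test of r gives power 79.2% at n = 18 and 81.4% at n = 19, so 19 is the smallest sufficient number.
- Dropout: 19 × 1.15 = 21.85, rounded to 22.

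The stated 19 and 22 are therefore reproduced with one pair of values per child. The point made here does not dispute them.

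**2. Effect of binning on the coefficient.** The documents give no BIS distribution, so every distribution below is assumed. BIS is rounded to whole numbers and limited to 0–98, the score has five levels, and the bins are the plan's. Each scenario uses 200,000 simulated pairs, treated as independent. Coefficients are absolute values.

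*Normal BIS within each score level* (five sets of level means × five mixes of levels × SD 8, 12, 15 = 75 scenarios). The change from recorded to binned Spearman ran from −0.063 to +0.023, with median −0.010. It rose in 11 of 75, at most from 0.747 to 0.770. A rise can occur when readings in one bin mostly share one score level, because binning then removes noise rather than signal.

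*Latent bivariate normal* (BIS mean 45–75 in steps of 5 × SD 10, 15, 20 × latent correlation 0.6–0.9 × five mixes = 420 scenarios). The coefficient always fell. The median fall was 0.01–0.03 with BIS centred at 55–75 and 0.04–0.10 with BIS centred at 45–50. The largest fall was 0.15.

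The share of readings below 50 drives this. With latent correlation 0.65 and equal score frequencies:

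| Readings below 50 | Recorded BIS | Plan's bins | Ratio | All cuts 5 lower |
|---|---|---|---|---|
| 4% | 0.613 | 0.599 | 0.98 | 0.593 |
| 15% | 0.613 | 0.600 | 0.98 | 0.600 |
| 36% | 0.614 | 0.586 | 0.95 | 0.596 |
| 49% | 0.614 | 0.560 | 0.91 | 0.584 |
| 67% | 0.614 | 0.504 | 0.82 | 0.557 |

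**3. Effect of the cut points alone.** In the table, moving every cut by 5 changes the binned coefficient by 0.00–0.01 with up to 36% of readings below 50, by 0.02 at 49% and by 0.05 at 67%.

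A second check used normal BIS with level means 93/80/60/45/38, shares 8/7/10/25/50%, SD 8 and 300,000 pairs. Recorded Spearman was 0.747. The plan's bins gave 0.769, and six bins cut at 45/55/65/75/85 gave 0.756. Cuts at 40/60/80 gave 0.720, but that is four bins, so it mixes number with placement. Reruns agreed to within about 0.003.

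**4. Power, only if 0.6 means recorded BIS.** One pair per child, two-sided 0.05. Fisher z: power = Φ(√(n − 3) × atanh r − 1.960). For n = 19 and r = 0.60 this is Φ(4 × 0.693 − 1.960) = Φ(0.81) = 79.2%.

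| r | n = 19, Fisher z | n = 19, t test (simulated) | n = 22, Fisher z | n = 22, t test (simulated) |
|---|---|---|---|---|
| 0.60 | 79.2% | 81% | 85.6% | 87% |
| 0.58 | 75.5% | 78% | 82.3% | 84% |
| 0.55 | 69.6% | 72% | 76.9% | 79% |

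These figures ignore the repeated readings within each child, for which the documents give no within-child correlation.

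**The case against.** The strongest reply concerns weight, not fact.

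- **The binning is disclosed.** The SAP names categories as the variable, and its boundaries are regular and stated. Spearman is valid for two ordinal variables, and nothing suggests boundaries chosen from the data. This stands: the coefficient is legitimate and reproducible, only coarser than it needs to be.
- **The information is used elsewhere.** The ANOVA uses BIS values, and the ROC analysis, which most directly answers whether BIS detects deep sedation, appears to do the same. This stands too, and it confines the point to one coefficient. Neither of those analyses reports a correlation, however.
- **The effect is mostly trivial.** Larger falls need BIS centred near 45–50. In the second cut-point check, the like-for-like six-bin shift is only 0.013 (0.769 to 0.756), and it is smaller still with SD 12 or 15. This is fair. Shifts of up to 0.05 appear only under the other assumed model, with most readings below 50.
- **The power figures do not describe the planned analysis.** They are conditional on the meaning of 0.6 and use one pair per child, whereas scores are taken every minute. If all 22 children contribute, a fall of 0.01–0.02 still leaves power above 80%. Correct; they show direction and rough scale only.
- **Pooling of repeated readings is a bigger problem.** Recorded BIS would not cure that, nor settle which observer's score is used. True, but these are separate matters and give no reason to bin.

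None of this supplies a reason for binning BIS in a rank correlation.

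**Conclusion.** The point holds and is minor. On the text it is certain: the one planned correlation uses six BIS categories although the number was recorded, and no reason is given for the binning or the boundaries.

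Its numerical consequence in this trial is unknown. It is probably a small attenuation, larger if about half or more of the readings fall below 50, and possibly a slight rise. That range rests entirely on assumed BIS distributions and on treating pairs as independent. Any loss of power arises only if the 0.6 was meant for recorded BIS; if it was meant for binned BIS, sizing and analysis agree. The ANOVA, kappa and ROC analyses are not called into question by this point.

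**What to change.** Replace the correlation sentence in the SAP with wording such as:

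> Spearman's rank coefficient is estimated between the BIS value as recorded (signal quality index ≥ 50) and each sedation score, for UMSS and MOAAS separately. The six BIS ranges serve only for description and for the kappa.

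If the binned coefficient is also reported, label it as binned and set it beside the unbinned one. In the sample-size paragraph, state whether the 0.6 refers to recorded or binned BIS.

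The cost is negligible. The numeric values are already in the data, so only the input variable changes and the other analyses stay as planned. Because the plan is written in the past tense, this may in practice mean re-running one analysis.
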